However, COPD is a heterogeneous and complex disease in which several factors combine to give the final clinical expression. Recent studies have shown that, despite being an extremely important parameter to predict the progression of the disease, FEV₁ is a poor marker for perception symptoms. In the study *Evaluation of COPD Longitudinally to Identify Predictive Surrogate Endpoints* (ECLIPSE), a large, 3-year, observational, multicentre, international study aimed at defining clinically relevant subtypes of COPD (8), the authors showed the complex interaction between FEV₁ and clinical markers. As a result, although clinical symptoms worsen as FEV₁ decreases in the patient cohort, when assessing patient-level data, the authors found varying degrees of deterioration in symptoms or exacerbations in all grades of COPD as measured by the severity of FEV₁ deterioration (9). From this and other similar analyzes, there is therefore a need to use new markers of clinical expression and disease progression that allow a correct, complete and more comprehensive evaluation of patients with COPD.

In recent years a change towards patient-centered medicine has been proposed and several initiatives have been presented to include other clinical variables in the so-called

multidimensional evaluation of COPD patients, in which FEV₁ continues to play a prominent role, but it is modulated by other clinical expressions of the disease (10). Consequently, since the 2011 update of the Global Initiative for Obstructive Pulmonary Disease (GOLD) document, it incorporates a three-pronged approach (pulmonary function, chronic symptoms and exacerbations) to identify the types of patients that may need different treatment strategies (11), as previously proposed (12). Although not without controversy (13), one of the strengths of this approach is the inclusion of the so-called patient reported outcomes (PRO), as part of the evaluation system. PRO have gained popularity as a measure of the impact of treatment from the perspective of patients, since they represent the individual's experience of their health status, beyond physiological limitations (14, 15). This multidimensional approach helps identify different types of patients and individualize pharmacological treatment.

However, COPD is a dynamic disease that evolves over time. Hence, research projects are needed to evaluate the behavior of the disease over time and allow clinicians to learn, longitudinally, how the disease behaves and what are the determinants that influence its clinical presentation and response to the treatments. For example, from the functional point of view, it is possible that other functional markers provide relevant information on the evaluation of the patient with COPD. In addition, other markers, such as peripheral blood eosinophils, have been proposed as a marker of response to various treatments (16). In this sense, cohort studies play an essential role (8, 17).

The TRACE project (Time-based Register and Analysis of COPD Endpoints) is part of this line of prospective and longitudinal observational study of patients with COPD with the idea of generating a cohort of patients who provide relevant information on the multidimensional behavior of the disease over time and the determinants of the different response to treatments. The added value that tries to provide TRACE over other previous cohorts is to observe the multidimensional impact of the disease over time, but using tools that are of the

usual clinical practice and that are available to all clinicians. In this way, its conclusions may be applied directly to the patient with COPD. The present document describes the full methodology of TRACE.

Methodology

TRACE is a prospective observational cohort study that will include patients diagnosed with COPD and followed up by our monographic COPD-dedicated outpatient clinic since 2012.

Inclusion criteria

Patients evaluated in the COPD-dedicated outpatient clinic since the year 2012 will be selected for longitudinal follow-up. The inclusion criteria are:

- Adult patients, both genders
- Aged 40-90 years.
- Diagnosed of COPD, according to the current recommendations (11, 18).
- Evaluated in our COPD-dedicated outpatient clinic since 2012
- Followed up by our team for at least 3 years.

Exclusion criteria

Another relevant comorbidity that conditions their care, as judged by the research team.

Sample size

Since the main objective of the project is to generate a cohort of patients, the total number of patients seen in one of our COPD-dedicated outpatient clinics during the year were to be selected through our electronic medical records system (SIDCA) at our institution. The number of patients seen for a consultation, in a year, is estimated at around 15 patients a day, for 4 days a week, for 48 weeks a year, a total of 2880 cases. Of these approximately 20% have alternative diagnosis to COPD, 20% are discharged at the first visit and we estimate a 10% loss

in follow-up. For this reason, we estimate an initial cohort of patients from 1440 cases with a minimum follow-up of 3 years.

Protocol

To include new cases, a retrospective review of patients who meet the inclusion / exclusion criteria will be done. For this, proceed as follows: the COPD-dedicated outpatient clinic of the principal investigator will be reviewed to evaluate all the patients that were evaluated in this consultation. Once identified, those who are still in follow-up will be selected and the data will be collected for inclusion. Subsequently, the patients included will be followed up prospectively with annual visits until their death or loss of follow-up, as per clinical practice in our institution.

Outcome measures

Primary outcome measures will be survival. Secondary outcomes measures include:

- Symptoms perception: dyspnea measured by mMRC scale (19)
- Number of moderate or severe exacerbations, defined as in the GOLD document (20)
- Time to first moderate or severe exacerbation
- FEV₁ annual decline
- Forced expiratory flow at 25-75% of expiration (FEF25-75)
- Peak expiratory flow (PEF)
- Peripheral blood eosinophils count expressed in cells/ μ L and in percentage of the white cell count
- Serum Alpha1-antitrypsin
- Total IgE
- Positive bronchial colonization
- Inhaled and oral COPD-related medication use

Registered data

The clinical data that will be collected at each annual visit include:

Filiation data:

- Gender
- Birth date

Previous history:

- - Smoking history
- - Comorbidities, collecting 4 indices: Charlson (21), COTE (22), COMCOLD (23) and Functional Comorbidity Index (24).
- History of COPD: type of disease according to GOLD (11) and the Spanish guideline: GesEPOC (18), updating the database with subsequent updates of these documents.

Current Anamnesis:

- Current symptoms: dyspnea according to the mMRC scale (19), cough, expectoration, self-listening wheezing
- Exacerbations in the previous year, as the patient remembers and recorded in his medical record.
- Current treatment, pharmacological and non-pharmacological. Compliance and adverse effects of the medication.

Complementary studies:

- Spirometry pre- and post-bronchodilation, collecting body mass index, forced vital capacity (FVC), FEV₁, FEV₁/FVC ratio, FEF25-75, and PEF.
- Alpha1-antitrypsin in serum
- Eosinophils in peripheral blood in absolute and relative values.
- Total IgE

- Sputum culture, spontaneous.

Follow-up status:

- Vital status
- Lost to follow up
- Date of end of follow-up
- Death caused by a respiratory condition

At each annual visit, the same information will be collected, updating the comorbidities index according to new clinical conditions that may occur.

Ethics

The present protocol has been approved by the Coordinating Committee of Ethics of the Biomedical Research of Andalusia (CCEIBA), Spain (approval acta 08/2015 and 07/2017), and it will observe the principles of the Declaration of Helsinki for research projects with human beings. During the study, the patient's personal data will not be collected as a study participant to identify the subject. The data obtained will be kept under strict confidentiality (Spanish Organic Law 15/1999, of protection of personal data) and only the principal investigator of the project will have access to them. Each case will be anonymous in the database and will be numbered with a code to guarantee the confidentiality of the data. In the database there will be no data that can identify patients. As this is an observational non-intervention study in which no diagnostic tests or therapeutic interventions of any nature will be performed outside of medical practice and given that the collected data will be anonymized, informed consent will not be requested. The ethical committee was aware of this circumstance and approved the procedure.

References

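### Is the planned cohort of 1440 undermined because it counts a year of clinic attendances as patients?

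*Protocol*

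**What the plan says.** The Sample size section gives the generation of a cohort as the main objective and sizes it from clinic activity. The quantity is introduced with "The number of patients seen for a consultation, in a year, is estimated" and calculated as "around 15 patients a day, for 4 days a week, for 48 weeks a year, a total of 2880 cases". The deductions follow in one sentence: "Of these approximately 20% have alternative diagnosis to COPD, 20% are discharged at the first visit and we estimate a 10% loss" to follow-up. The result is worded as an estimate: "we estimate an initial cohort of patients from 1440 cases with a minimum follow-up of 3 years".

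Three other places bear on the number.

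- **Inclusion criteria.** Eligibility is not limited to one year: "Evaluated in our COPD-dedicated outpatient clinic since 2012". At least three years of follow-up by the team is also required.
- **Protocol subsection of the Methodology.** All patients evaluated in the clinic are reviewed, and those under follow-up at that time are taken into the cohort. They are then seen yearly until death or loss, which is described as the institution's normal practice.
- **Outcome measures, and the SAP.** Survival is primary. It is analysed by Kaplan-Meier curves, log-rank tests and Cox regression at the 0.05 level. Neither document states a power, an effect size or a required number of deaths.

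**The concern.** Patients per day multiplied by clinic days is, on its face, a count of attendances. It equals a count of people only if nobody attends twice in the year, and this clinic follows its patients over time. Four features look wrong:

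1. There is no visits-per-patient factor.
2. The three percentages are added to 50%, although loss to follow-up can occur only among patients who were not already excluded or discharged.
3. The 1440 are said to have three years of follow-up, yet deaths are not deducted. The protocol names death and loss separately, so the 10% cannot be assumed to cover both.
4. The count covers one year, while eligibility runs from 2012.

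This is the only planning number in either document, and survival is the primary outcome. The number of distinct patients drives the number of deaths, and deaths determine the precision of the survival curves and how many covariates a Cox model can carry. A cohort half the stated size would be a materially weaker study. A list built from attendances could also hold the same patient twice.

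**Working it through.** **Inputs from the Sample size section:** 15 patients a day; 4 days a week; 48 weeks a year; 20% with an alternative diagnosis; 20% discharged at the first visit; 10% lost to follow-up. **Not given in the documents:** mean visits per patient per year (v) and the proportion dying before three years (m). Both are treated below as assumptions.

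**Step 1. Reproduce the stated figures.**

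- 15 × 4 × 48 = 2880.
- 2880 × (1 − 0.20 − 0.20 − 0.10) = 2880 × 0.50 = 1440.

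Both agree exactly, so there is no arithmetical slip.

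**Step 2. Change only the way the percentages combine.**

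- The two 20% shares on the full base, then 10% of the remainder: 2880 × 0.60 × 0.90 = 1555 (+8%).
- Fully sequential: 2880 × 0.80 × 0.80 × 0.90 = 1659 (+15%).

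If summing is an error, it makes the estimate too low. It need not be an error. The wording "Of these approximately 20% have alternative diagnosis to COPD" places the first share on the 2880. If the other two shares refer to the same base and to separate groups, adding them is correct.

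**Step 3. Allow for repeat visits, without deaths.** Divide each total by v.

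| v (assumed) | Summed | 10% of remainder | Sequential |
|---|---|---|---|
| 1 | 1440 | 1555 | 1659 |
| 1.5 | 960 | 1037 | 1106 |
| 2 | 720 | 778 | 829 |

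The only visit frequency in the documents is yearly. It describes patients already included, so it does not prove v = 1, but it is compatible with a value near 1. Much higher values are harder to sustain. If the 20% discharged at the first visit attend once, an overall mean of 2 requires (2 − 0.2)/0.8 = 2.25 visits a year from everyone else, and a mean of 3 requires (3 − 0.2)/0.8 = 3.5.

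**Step 4. Allow for deaths, at v = 1.** Multiply each total by (1 − m).

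- m = 10%: 1296, 1400 and 1493 in the same column order.
- m = 20%: 1152, 1244 and 1327.

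**Step 5. Find where the effects cancel.**

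- The sequential total returns to 1440 at v = 1659/1440 = 1.15 with no deaths, or at m = 1 − 1440/1659 = 13.2% with one visit each.
- The 1555 total returns to 1440 at v = 1.08, or at m = 7.4%.

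Modest repeat attendance or modest mortality therefore offsets the gain from sequencing and leaves the stated figure about where it is.

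**Step 6. Consider the period.** The calculation uses one year of activity, while recruitment draws on patients seen since 2012. More than one year of new patients can only raise the number. The documents do not give new patients per year, so the gain cannot be fixed.

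**Step 7. Ask what depends on 1440.** No power statement, confidence-interval width, event target or stopping point refers to it. The record review, not the multiplication, identifies the patients, and it admits all who qualify. The cohort size, the number of deaths and the Cox model are the same whether the paragraph says 1440, 960 or 1659.

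**The case for a change.** The strongest argument for acting needs no assumed visit rate. The share "20% are discharged at the first visit" is taken off all 2880, which makes sense only if all 2880 are first visits. At constant throughput, 1440 retained patients seen once a year fill 1440 of the 2880 places and leave at most 2880 − 1440 = 1440 for newcomers. A first-visit discharge rate then cannot apply to the whole base, even at exactly one visit per patient. In addition, patients who died before three years never enter the cohort, and neither the comorbidity exclusion nor the age limits are deducted. The remedy would be cheap: a count of distinct patients from the record system that the protocol already names.

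As a criticism of the reasoning, this stands. The base of each percentage is unclear, and 1440 cannot be verified from the documents. It does not show that 1440 is too high. If 1440 places a year go to newcomers and the protocol's own 50% is retained, one year yields 720 patients and two years yield 1440 again; eligibility reaches back to 2012. That is an illustration, not an estimate, but it shows that correcting the base and correcting the period work against each other.

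The risk of duplicates does not follow from the calculation. The multiplication is a forecast; the protocol selects patients, and each case is coded individually in the database. The cheap query is in substance the record review that the protocol already plans. An analyst reporting the cohort would give the number of distinct patients found and the reasons for exclusion in any case.

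One related matter should be kept apart. Requiring three years of survival and continuing follow-up before entry may affect how survival results are interpreted. That is a question about the definition of the cohort, and a revised headcount would not address it.

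**Conclusion.** No change to the plan is needed. The paragraph is a rough feasibility estimate whose assumptions are not written down. Its arithmetic is exact. The documents do not show that the figure is wrong, and they do not settle the direction of any error.

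With v between 1 and 2 and no deaths, the plausible readings run from 720 to 1659. With 20% dying before three years, the lower end falls to 720 × 0.80 = 576. These ranges rest on assumed visit rates and mortality, and they leave out the additional years of intake, which would raise every figure.

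The concern is right that the forecast lacks a visits-per-patient factor, a separate allowance for deaths and a period that matches the eligibility criteria. These are missing details in a number on which nothing else depends. The actual count will come from the planned record review, and precision will be set by the deaths observed in that cohort. Rewriting the forecast would add documentation but would change no enrolment decision, analysis or conclusion. The judgement would differ if a power claim, an event target or a limit on enrolment rested on 1440; neither document contains one.

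### The plan does not say how exacerbations between the last annual visit and death or loss are collected, or whether a fatal one counts; read literally, they are under-counted in patients who die

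*Protocol*

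**What the plan says.** Under *Outcome measures*, the protocol makes survival primary ("Primary outcome measures will be survival"). Two of its eleven secondary outcomes concern exacerbations: the number that are moderate or severe, and "Time to first moderate or severe exacerbation".

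Under *Protocol* (within Methodology), "the patients included will be followed up prospectively with annual visits until their death or loss of follow-up". The *Registered data* list opens with "The clinical data that will be collected at each annual visit include". Within it, under *Current Anamnesis*, the exacerbation item reads "Exacerbations in the previous year, as the patient remembers and recorded in his medical record".

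The *Follow-up status* fields are vital status, loss to follow-up, "Date of end of follow-up" and "Death caused by a respiratory condition". None concerns exacerbations.

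The SAP plans paired t tests or McNemar tests for follow-up data, regression models for the risk of future events, and Kaplan-Meier, log-rank and Cox analyses for survival. It gives no person-time, censoring or death rule for the exacerbation outcomes.

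**The concern.** A patient who dies between two visits has no later visit at which the previous-year look-back is made. The months before death then have no stated collection point for exacerbations, although the death and its date are recorded. The same holds for the interval before loss to follow-up. This gap remains even if the item is completed perfectly at every attended visit.

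The missing interval depends on the primary outcome, because it falls on those who die. Two things are at stake. Exacerbation counts in these patients would be too low. In addition, a patient whose first exacerbation during follow-up is fatal could enter the data as a respiratory death with no exacerbation event, so that censoring that patient for time to first exacerbation would be informative.

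**Working it through.** **The plan's own figures.** The documents give no exacerbation rate and no death rate. The only figure to reproduce is the cohort size: 15 × 4 × 48 = 2880, and 2880 × (1 − 0.20 − 0.20 − 0.10) = 1440, as stated. Nothing below depends on it.

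**Inputs.** Annual visits and the previous-year look-back come from the protocol. The following are assumptions:

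- The patient completes *m* annual look-backs after inclusion and then dies at a time uniform over the next year, so a mean of 0.5 year is not covered.
- The exacerbation rate in that last interval is *k* times the earlier rate, with *k* = 1, 2 or 3.
- Nothing is collected for that interval (the literal reading).

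**Share of events missed.** In units of the earlier yearly rate, *m* events are counted and *m* + 0.5*k* occur on average. The share missed is 0.5*k* / (*m* + 0.5*k*).

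| Look-backs *m* | *k* = 1 | *k* = 2 | *k* = 3 |
|---|---|---|---|
| 1 | 0.5/1.5 = 33% | 1.0/2.0 = 50% | 1.5/2.5 = 60% |
| 2 | 0.5/2.5 = 20% | 1.0/3.0 = 33% | 1.5/3.5 = 43% |
| 3 | 0.5/3.5 = 14% | 1.0/4.0 = 25% | 1.5/4.5 = 33% |
| 5 | 0.5/5.5 = 9% | 1.0/6.0 = 17% | 1.5/6.5 = 23% |

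**Effect on rates.** This depends on the denominator, which the SAP does not give.

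- *Person-time to death, constant rate.* If survivors are fully observed, the ratio of the rate in patients who die to that in survivors is multiplied by *m* / (*m* + 0.5): 0.67 at *m* = 1, 0.80 at *m* = 2, 0.86 at *m* = 3 and 0.91 at *m* = 5. At *m* = 3, a true ratio of 1.0 appears as 0.86, 1.5 as 1.29 and 2.0 as 1.71.
- *Person-time to the last visit, constant rate.* There is no bias in the rate.
- *Person-time to the last visit, rising rate.* The rise is lost. At *m* = 3 and *k* = 3, the true average rate is 4.5/3.5 = 1.29 times the earlier rate, but it is recorded as 1.0 times.

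**Time to first exacerbation.** Take 1 exacerbation per year, a Poisson process and a missed interval of exactly half a year. The chance of no event before the last visit is e^−2 = 13.5% at *m* = 2 and e^−3 = 5.0% at *m* = 3. The chance of at least one event in the missed half-year is 1 − e^−0.5 = 39% (*k* = 1) to 1 − e^−1.5 = 78% (*k* = 3). The product is about 5–11% of patients dying at 2.5 years and 2–4% of those dying at 3.5 years whose first event is missed. Overdispersion or another base rate would change these figures.

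**The case against.** The strongest reply is that the exacerbation item names the medical record as well as the patient's memory, and the record can still be read after death. Vital status and respiratory death stand in the same annual-visit list, yet for a patient who has died they can only be completed without attendance. Some closing step is therefore implied, and nothing forbids reading exacerbations at that step. This stands: a reader might infer that these events are never counted, and the text does not support that. What remains is that the protocol presents itself as the complete account of the methods, and it gives the team no instruction to collect them.

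Other stronger readings also fail:

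- *Patients who die would appear to exacerbate less than survivors.* Only less than they really did is supportable, and only under non-collection. At three visits with person-time to death, a true ratio of 1.5 still appears as 1.29.
- *Follow-up time for exacerbations runs to death.* No passage says so.
- *The link between exacerbations and survival is generally biased towards none.* Exacerbation history recorded at a visit and used to predict later death is measured before the outcome, so the last interval is not needed.
- *Survivors lose nothing.* That holds only if their time ends at a visit. If it runs to a data cut-off, they too have an open interval.
- *A fatal exacerbation is recorded only as a respiratory death.* The two fields are not mutually exclusive. The plan simply has no rule.

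**Conclusion.** The point holds as a gap in outcome collection whose effect depends on the primary outcome. Following the list literally leaves the interval before death or loss uncollected for two secondary outcomes. Under the stated assumptions, 14–33% of a deceased patient's exacerbations are missed after three visits and 20–43% after two; the wider range for one to five visits is 9–60%. The direction of the error in counts is certain once non-collection is granted. The error in rates depends on the unstated denominator and on whether the rate rises before death.

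The primary outcome is unaffected. No cohort-level effect can be given, because the documents state neither death nor exacerbation rates. This is an inexpensive improvement that should be made, and it does not undermine the study's main analysis.

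**What to change.** 1. **Protocol, *Follow-up status*.** When follow-up ends, extract from the medical record every moderate or severe exacerbation, with its date, from the last annual visit to death or last contact.
2. **Protocol, *Outcome measures*.** State that an exacerbation admission ending in death counts as a severe exacerbation event as well as a respiratory death.
3. **SAP.** Where no record is available after the last visit, end exacerbation person-time and censor time to first exacerbation at that visit, for survivors and deceased patients alike.

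The cost is one extra record extraction per patient who dies or leaves, plus a few sentences of text; no visit or test is added. The plan does not state the source used for vital status and cause of death, so it cannot be assumed that the same look-up already provides these data. Exacerbations treated elsewhere may still be missed, and where the third rule has to be used, a rise in rate before death is still not seen.

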STATISTICAL PLAN**Time-based Register and Analysis of COPD Endpoints (TRACE).****NCT number:** NCT03485690**Date:** February 2nd, 2018**Scientific committee:**

[name]

[name]

[name]

[name]

[name]

[name]

Institutions:

(1) Centro de investigación biomédica en red de enfermedades respiratorias (CIBERES).

Instituto de Salud Carlos III, Madrid Spain

(2) Unidad Médico-Quirúrgica de Enfermedades Respiratorias, Instituto de Biomedicina de

Sevilla (IBiS), Hospital Universitario Virgen del Rocío/Universidad de Sevilla, Seville,

Spain

Statistical plan

The data will be analyzed using the software IBM SPSS Statistics (IBM corporation, Armonk, New York). For the description of the variables, centralization and dispersion estimators appropriate to the nature of each variable and its distribution will be used. The differences between baseline patient types will be analyzed using the Student's t test for independent data (after checking the equality of the variances with the Levene test) or using the Chi-square test (with Fisher's correction if applicable) for qualitative variables. Follow-up studies will be done using the Student's t test for paired data or with the McNemar test for categorical variables. Potential associations found in this bivariate analysis will be further evaluated via a multivariate study depending on the nature of the analysis. Accordingly, the calculation of the relative risk of future events will be adjusted from multiple regression models. Survival analysis will be carried out by Kaplan-Meier curves with log-rank test to assess differences between potential patient groups. Potential associations will be further explored by Cox proportional hazards regression analysis. The level of statistical significance is set at 0.05.

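### The exacerbation item looks back a fixed year at visits with no timing rule, so a late, early or missed visit leaves time uncovered or covered twice for first-event times and cumulative counts

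*Protocol*

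**What the plan says.** The protocol's Registered data section opens with "The clinical data that will be collected at each annual visit include", and the exacerbation item under Current Anamnesis reads "Exacerbations in the previous year, as the patient remembers and recorded in his medical record". The one-year window appears to govern both sources, the patient's memory and the medical record. The section closes by saying that the same information is collected at every annual visit, so the window does not adapt to the time actually elapsed.

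The Protocol section says that patients will be "followed up prospectively with annual visits until their death or loss of follow-up, as per clinical practice in our institution". The planned interval and the look-back therefore match by design. No tolerance around 12 months is given, and nothing says what happens after an early, late or missed visit.

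Two secondary outcomes draw on this item: the number of moderate or severe exacerbations, for which no period or denominator is stated, and "Time to first moderate or severe exacerbation". The only dates listed among the registered data are the birth date and "Date of end of follow-up". Neither a visit date nor an exacerbation date is listed.

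The SAP says "Follow-up studies will be done using the Student's t test for paired data or with the McNemar test for categorical variables". It also provides Kaplan-Meier curves, log-rank tests and Cox regression. It names no exposure time for exacerbations, no rule for overlapping periods and no method for events known only to lie in an interval.

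**The concern.** A fixed 12-month look-back covers follow-up without gap or overlap only if visits are exactly 12 months apart. If the visit comes at 15 months, no visit asks about the first 3 months. If it comes at 9 months, 3 months are asked about twice; at the first follow-up visit those 3 months lie before inclusion, so an older event can be taken as new. If a visit is missed, a whole year goes unasked.

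Time to first exacerbation needs continuous coverage from its origin. An event in a gap either disappears, leaving the patient apparently event-free, or is replaced by a later event. A count added up over follow-up needs every month covered once. Both needs apply to a cohort followed for at least 3 years, and nothing in the plan would detect or correct a mismatch.

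**Working it through.** No planning figure in the documents bears on this point. The only one is the cohort size (15 × 4 × 48 = 2880; 2880 × (1 − 0.20 − 0.20 − 0.10) = 1440), which is not used below.

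**Inputs from the documents:** look-back of 12 months (Registered data); nominal interval of 12 months with no tolerance (Protocol section).

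**Assumptions:** actual interval L in months; exacerbation rate r per year, constant over time, with a range of 0.5 to 1.5. The documents give neither.

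**Summed count.** Expected events counted at a visit are r × 12/12 = r. Expected true events in the interval are r × L/12. The ratio of counted to true is 12/L.

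| L (months) | Uncovered (months) | Covered twice (months) | Counted/true |
|---|---|---|---|
| 9 | 0 | 3 | 12/9 = 1.33 |
| 11 | 0 | 1 | 12/11 = 1.09 |
| 12 | 0 | 0 | 1.00 |
| 13 | 1 | 0 | 12/13 = 0.92 |
| 15 | 3 | 0 | 12/15 = 0.80 |
| 24 (one missed visit) | 12 | 0 | 12/24 = 0.50 |

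Dividing the existing count by the visit interval does not repair this. The numerator still covers 12 months while the denominator covers L, so the estimated rate is again 12/L of the truth.

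**Count per recalled year.** Each visit contributes r expected events over one recalled year. The ratio is 1.00 for every L, provided that the rate is constant and visit timing is unrelated to exacerbations.

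**Early and late visits together.** In a simulation with three intervals per patient, each spread evenly within ±2 months of 12, about 4% of time is uncovered and about 4% is covered twice. The mean summed count has a net ratio of 1.00. The errors cancel in the cohort mean but not within a patient.

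**First event.** The chance that the first event after a visit falls in the uncovered start of the next interval is 1 − exp(−r × (L − 12)/12). For L = 15 the gap is 0.25 years:

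- r = 0.5: 1 − exp(−0.125) = 12%
- r = 1.0: 1 − exp(−0.25) = 22%
- r = 1.5: 1 − exp(−0.375) = 31%

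For L = 13 and r = 1.0 it is 1 − exp(−1/12) = 8%. The early-visit error has the same form: at r = 1.0, a first follow-up visit at 9 months has a 22% chance that its 3 overlapping months contain an event from before inclusion.

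**The case against.** The strongest reply is that visits are planned as annual, so the look-back fits the schedule and a mismatch is a departure from it. The documents give no data on how often or how far visits depart. This stands, and it is why every interval above is labelled an assumption. It does not remove the point, because timing is left to routine practice with no tolerance and the item covers follow-up exactly only at exactly 12 months.

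A reader might infer that any interval other than 12 months biases the exacerbation count. The documents do not support that. They never say that yearly counts will be summed, and the SAP's paired comparison could set one 12-month count against another, like for like. Per recalled year the ratio is 1.00 under the conditions above. What remains is that the count outcome has no stated period, so a cumulative reading is not excluded, and that time to first exacerbation gains nothing from the per-year argument.

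A reader might also infer that contrasts between patient groups are inflated. If frequent exacerbators came every 9 months and others every 15, a ratio of summed rates would be inflated by 1.33/0.80 = 1.67. None of the three ingredients is documented: those intervals, a link between visit timing and exacerbations, or summation. The 1.67 illustrates an extreme pair and does not estimate a bias in this study.

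Two further replies are partly right. The medical record could supply the missing events, but the item limits it to one year and lists no event dates. And the absent event date is the larger defect for time to first exacerbation, since a yearly count places an event only within a year even when visits are punctual. Dating events only within the previous year would still leave the gap after a late visit, so the window needs its own correction.

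**Conclusion.** The concern holds in a limited form. The fixed look-back, combined with visits that have no window or late-visit rule, can bias time to first moderate or severe exacerbation and any count accumulated over follow-up. The previous-year count analysed as an annual rate is largely safe if visit timing is unrelated to exacerbations.

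The size depends on intervals and rates that the documents do not give. A departure of one month either way moves a summed count by 8% to 9%, a 15-month interval lowers it by 20%, and one missed visit halves it for that interval. The 12% to 31% for a hidden first event applies to patients who have a 3-month gap and are still event-free when it begins, at constant rates of 0.5 to 1.5 a year; it is not a share of the whole cohort. The outcomes affected are secondary, and the change is cheap enough to be worth making.

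**What to change.** Keep the previous-year count at every visit. It is the right measure for like-for-like paired comparisons, and it can inform the GOLD typing that the protocol also registers.

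Add a second item: moderate or severe exacerbations since the last recorded visit, taken from the medical record for the whole interval, including any period spanned by a missed visit. Record the date of each event and the dates of both visits. The record should be the main source, because patient recall weakens beyond a year.

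In the SAP, state that time to first exacerbation uses the dated events. State also that any cumulative count uses the since-last-visit item in a rate model, with the log of the actual interval as offset. Before recording error, the ratio of counted to true events is then 1.00 at every interval.

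The cost is one added field with its dates, a query of the record between two visit dates, and a rate model in place of the paired t test for the cumulative count, because exposure then differs between visits. Nothing already collected is removed.
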